2.2.2. Part 2 Dose Expansion

Part 2 dose expansion will include 2 arms: Arm 1 will enroll approximately 60 patients with NSCLC who progressed on or were intolerant to systemic therapy or for whom systemic therapy was refused or unavailable but have not previously received anti-PD-1 or anti-PD-L1. Arm 2 will enroll approximately 40 patients with urothelial carcinoma who progressed on or were intolerant to systemic therapy or for whom systemic therapy was refused or unavailable but have not previously received anti-PD-1 or anti-PD-L1. All patients in Part 2 will receive 300 mg PF-06801591 SC q4w. The 300 mg SC dose level in Part 2 was selected based upon safety, PK, PD, and preliminary anti-tumor activity observed in Part 1, as well as the maximum injection volume considered feasible with the current formulation.

After the first 30 NSCLC patients have been enrolled and have either completed their first tumor assessment (at approximately 8 weeks post treatment), or have discontinued from the study before their first scheduled tumor assessment, preliminary assessment of safety and efficacy data maybe completed. This preliminary data may provide guidance in the decision to the increase or decrease the sample size of each arm, to add other tumor types in a future amendment, or to initiate additional clinical studies. The specific details for this data look are described in Section 7.

3. ENDPOINTS AND COVARIATES: DEFINITIONS AND CONVENTIONS

3.1. Primary Endpoint(s)

Part 1:

- *DLTs at escalated doses of PF-06801591.* The specific definition of DLT is provided in the study protocol.
- Adverse Events (AEs) as characterized by type, frequency, severity (as graded by National Cancer Institute Common Terminology Criteria for Adverse Events [NCI CTCAE] version 4.03), timing, seriousness, and relationship to study therapy PF-06801591.
- Laboratory abnormalities as characterized by type, frequency, severity (as graded by NCI CTCAE version 4.03), and timing.

Part 2:

- AEs as characterized by type, frequency, severity (as graded by NCI CTCAE version 4.03), timing, seriousness and relationship to study therapy PF-06801591 *administered by SC administration.*
- Laboratory abnormalities as characterized by type, frequency, severity (as graded by NCI CTCAE version 4.03) and timing.
- ORR as assessed using RECIST version 1.1 and irRECIST. ORR is defined as the proportion of patients who achieved completed response (CR) or partial response (PR) per RECIST 1.1, or irRECIST.

3.2. Secondary Endpoint(s)

Part 1:

- PK parameters of PF-06801591: Cycle 1 and Cycle 4 C_{max} , area under the concentration versus time curve (AUC) from time zero to the last quantifiable time point prior to the next dose (AUC_{last}), and if data permit, CL, V_d , volume of distribution at steady state (V_{ss}), accumulation ratio (Rac) when feasible, and terminal elimination $t_{1/2}$.
- Incidence of anti-drug antibodies (ADA) and neutralizing antibodies (NAb) against PF-06801591.
- PD-1 receptor occupancy (RO) by PF-06801591, as assessed by measuring the levels of unbound (free) cell surface PD-1 on circulating T cells over time following PF-06801591 administration.
- Objective tumor response, as assessed using the Response Evaluation Criteria in Solid Tumor (RECIST) version 1.1 and immune-related RECIST (irRECIST); and proportion of subjects with PR (and irPR, as appropriate).
- Time-to-event endpoints based on RECIST and irRECIST and PFS (and irPFS as appropriate), Duration of stable disease (DOSD, or irDOSD as appropriate), and Duration of response (DOR, or irDOR as appropriate).
 - PFS is defined as the time from treatment start date to date of first documentation of progression or death due to any cause.
 - Duration of stable disease is defined from the start of the treatment until the criteria for progression are met, taking as reference the smallest tumor measurements recorded since the treatment started, including the baseline measurements. This endpoint is applicable to the subset of patients who achieved a best overall response of stable disease (SD), those patients whose best overall response is not SD will be excluded from this endpoint analysis. A minimum of 6 weeks (with a - 5 days window, which is essentially a minimum of 35 days) interval of two assessments is required for this endpoint.
 - Duration of response is defined as the time from start date (which is the date of first documentation of PR or CR) to date of first documentation of objective progression or death. DOR is only applicable to those patients with an objective response.

Part 2:

- Time to event endpoints by PF-06801591 administered by SC based on RECIST and irRECIST, including time to response (TTR) and time to progression (TTP) as well as PFS (and irPFS as appropriate), DOSD (and irDOSD as appropriate), and DOR (and irDOR as appropriate). Time to response is defined as the time from the study treatment date to the first documentation of PR or CR. Time to progression is the time from start date to date of first documentation of objective progression.
- *Median time to death, proportion of patients alive at 6 months, 1 year, and 2 years.* Time to death (i.e. overall survival) is the time from treatment start date to date of death due to any cause.
- Trough PF-06801591 concentrations for selected cycles.
- Incidence of ADA and NAb against PF-06801591 administered by SC.

CCI

Detailed descriptions of Endpoints are provided in [Appendice 9.1](#), [9.4](#), and [9.5](#).

CCI

4. ANALYSIS SETS

4.1. Full Analysis Set

The full analysis set includes all enrolled patients. This is equivalent to the ITT (intent-to-treat) population.

4.2. Safety Analysis Set

The safety analysis set includes all enrolled patients who receive at least one dose of study medication.

4.3. 'PER PROTOCOL' Analysis Set

The per protocol analysis set includes all enrolled patients who received at least one dose of study treatment and who did not have major treatment deviations during the Cycle 1. For the IV administration of PF-06801591, patients with major treatment deviations in the 21-day DLT observation period are not evaluable for the MTD assessment and will be replaced as needed to permit MTD estimation.

For the SC administration of PF-06801591, patients with major treatment deviations in the 28-day observation period will not be evaluable for DLT.

Major treatment deviations include:

- Administration of <50% of the planned dose of PF-06801591, provided that the reduction is not due to toxicity attributable to PF-06801591.
- Administration of >150% of the planned dose of PF-06801591.

4.4. PK Analysis Set

4.4.1. PK Concentration Set

The PK concentration population is defined as all patients who receive PF-06801591, have no protocol deviations affecting the PK assessment, and have at least 1 post-dose concentration measurement.

4.4.2. PK Parameter Set

The PK parameter analysis population is defined as all enrolled patients treated who have sufficient information to estimate at least 1 of the PK parameters of interest.

4.5. PD Biomarker Analysis Set

The biomarker analysis set includes all enrolled patients with at least one of the pharmacodynamic/biomarker parameters evaluated at pre- and/or post-dose.

4.6. Modified Intent-to-Treat Set

The modified intent-to-treat (mITT) population is defined as all the randomized subjects who have received at least 1 dose of study medication, have measurable disease baseline assessment (within 28 days prior to study entry) and at least 1 post baseline assessment or disease progression, global deterioration of health status, or death. The mITT population will be used for anti-tumor assessment.

4.7. Immunogenicity Analysis Set

The immunogenicity analysis set is defined as patients who receive at least 1 dose of study treatment and have at least 1 ADA or NAb sample collected.

4.8. Treatment Misallocations

Subjects who receive the wrong initial dose for whatever reason will be analyzed according to the initial dose actually received. Subjects who receive the wrong dose after the initial dose will be analyzed according to the initial dose received.

4.9. Protocol Deviations

The determination of protocol deviations (PDs) and important protocol deviations (IPDs) will follow Pfizer standard operating procedures. A full list of PDs, IPDs, and IPDs that are excluded from Per-protocol analysis will be determined prior to the database release and be included in the CSR.

5. GENERAL METHODOLOGY AND CONVENTIONS

This is an open-label dose escalation study and no interim analysis or blinding is planned for this study.

5.1. Statistical Hypotheses

There are no statistical hypotheses.

5.2. Statistical Decision Rules

5.2.1. Part 1 (MTD Finding)

Part 1 dose escalation phase of this study employs an mTPI design to estimate the MTD. The mTPI design employs a simple beta-binomial model with prior a conjugated prior beta (0.5, 0.5). Decision rules are based on calculating the unit probability mass (UPM) of 3 intervals corresponding to underdosing, proper dosing, and overdosing in terms of dose limiting toxicity. A proper dosing interval is centered at the target toxicity rate (pT) of 27.5% with 5% uncertainty (0.225 < pT < 0.325). The under dosing interval is (0, 0.225), and the overdosing interval is (0.325, 1). The 3 dosing intervals are associated with 3 different dose escalation decisions. The underdosing interval corresponds to a dose escalation (E), overdosing corresponds to a dose de-escalation, and proper-dosing corresponds to staying at the same current dose. Given an interval and a probability distribution, the UPM of that interval is defined as the probability of the interval divided by the length of the interval. The mTPI design calculates the UPMs for the 3 dosing intervals, and the one with the largest UPM implies the corresponding dose-finding decision. That decision provides the dose level to be used for future patients. For example, if the underdosing interval has the largest UPM, decision E (to escalate) will be executed, and the next cohort of patients will be treated at the next-higher dose level. Under the mTPI design, a trial is terminated when either the lowest dose is above the MTD or a pre-specified maximum sample size for Part 1 (approximately 40) is reached.

The following table shows the probability of escalating to the next dose level for a range of underlying true DLT rates. For example, for a cohort size of n=3 and for a DLT that occurs in 10% of patients, there is a greater than 90% probability of escalating. Conversely, for a DLT that occurs with a rate of 70%, the probability of escalating is 3%. It is assumed that dose escalation occurs with either 0/3 or 1/6 patients with DLTs.

Probability of Escalating Dose									
True underlying DLT rate	10%	20%	30%	40%	50%	60%	70%	80%	90%
Probability of escalating	0.91	0.71	0.49	0.31	0.17	0.08	0.03	0.009	0.001

5.2.2. Part 2 (Dose Expansion)

Part 2 (N=100) of this study is intended to further characterize the safety, efficacy, PK, PD, and immunogenicity profiles of 300 mg of SC PF-06801591 in anti-PD-1 or anti-PD-L1 treatment naïve patients with NSCLC (N=60) and urothelial carcinoma (N=40) who have progressed on or were intolerant to systemic therapy or for whom systemic therapy was refused or unavailable.

Summary statistics will be provided for trough PF-06801591 concentrations, safety endpoints, immunogenicity, pharmacodynamic/biomarkers, and efficacy data.

When the first 30 NSCLC patients have been enrolled and have either completed their first tumor assessment (at approximately 8 weeks post treatment), or have discontinued from the study before their first scheduled tumor assessment, preliminary assessment of safety and efficacy data may be completed. This preliminary data may provide guidance in the decision to increase or decrease the size of each arm, to add other tumor types in a future amendment, or to initiate additional clinical studies.

5.2.3. Sample Size Determination

The exact sample size for the dose escalation design in Part 1 cannot be specified in advance due to the dynamic features of mTPI. For the first dose level (0.5 mg/kg IV), in the absence of actual DLTs, a total of 2 patients will be enrolled: 2 patients in Part 1A and no patient in Part 1B. For subsequent dose levels it is anticipated that approximately 2 to 4 patients will be enrolled in Part 1A and approximately 2 to 5 patients in Part 1B with available pre- and on-treatment biopsies for IHC testing and up to 9 patients at dose levels 1, 3, and 10 mg/kg administered by IV in Part 1. A single cohort with SC administration at a dose level of 300 mg of PF-06801591 will be opened for enrollment shortly after the cohort at a dose level of 3 mg/kg IV in Part 1A will have completed enrollment and the 21-day DLT observation period. This cohort at a dose level of 300 mg SC will seek 2 to 4 patients in Part 1A, up to 11 patients in Part 1B with available pre- and on-treatment biopsies for IHC testing, and up to 15 patients in Part 1. The actual Part 1 sample size may be smaller, depending on the underlying dose toxicity profile, and the number of dose levels studied.

Part 2 of the study will enroll approximately 60 patients with NSCLC who progressed on or were intolerant to systemic therapy or for whom systemic therapy was refused or unavailable and are treatment naïve for anti-PD-1 or anti-PD-L1. NSCLC was selected for historical comparability to prior large anti-PD-1 studies and dosing of 300 mg SC in Part 2 has been selected based on safety, PK, available biomarker data and preliminary anti-tumor activity from Part 1. There is no hypothesis testing in Part 2. Estimation approach is used to characterize the precision of response data. The estimation of ORR using N=60 is described as follows. Suppose that the ORR estimate is 19% in Part 2 with N=60, then the 80% and 90% confidence intervals of the true ORR will be (13.3, 26.3%) and (12.1, 28.6%) respectively. Note that an ORR of 19% was observed in a clinical trial for nivolumab in previously treated NSCLC patients. In Part 2, approximately 40 urothelial cancer patients will also be enrolled, the sample size is based on clinical considerations of expanding the safety database.

5.3. General Methods

Whilst every effort has been made to pre-specify all analyses in this statistical analysis plan, if any additional exploratory analyses be found to be necessary, the analyses and the reasons for them will be detailed in the clinical study report (CSR).

Unless otherwise specified, the baseline value is defined as the value collected at the time closest to, but prior to, the start of study drug administration in the first cycle. All data will be categorized

based on the scheduled visit at which it was collected. These visit designators are predefined values that appear as part of the visit tab in the eCRF.

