- j. **Triplicate 12-Lead Electrocardiogram (ECG):** See Assessment [Section 7.1.5](#). ECGs will be collected at times specified in the [Schedule Of Activities](#). The Screening ECG will be a single 12-lead ECG. At all other times, at each time point, 3 consecutive 12-lead ECGs (triplicate) will be performed approximately 2 minutes apart to determine mean QTcF interval. All 12-lead ECGs should be confirmed by a qualified person at the institution and will be reviewed by a central laboratory. ECGs on Day 1 of each cycle will be collected prior to dosing, and at the end of infusion (approximately 1 hour) following administration of each dose of PF-06801591. When coinciding with blood sample draws for PK, ECG assessment should preferably be performed prior to blood sample collection, such that the blood sample is collected at the nominal time. If the mean QTcF is prolonged (≥ 45 msec from the pre-dose baseline, or > 500 msec), the ECGs should be re-evaluated by a qualified person at the institution for confirmation. Additional triplicate ECGs may be performed as clinically indicated.
- k. **Hematology:** See Assessments [Section 7.1.3](#) for Laboratory Tests list. Assessments and physician's evaluation must be performed prior to dosing. No need to repeat on C1D1 if baseline assessment performed within 72 hours prior to that date. Assessments performed on C2D1 and each subsequent cycle should be performed within 48 hours prior to dosing.
- l. **Blood Chemistry:** See Assessments [Section 7.1.3](#) for Laboratory Tests list. No need to repeat on C1D1 if screening assessment performed within 72 hours prior to that date. Assessments and physician's evaluation should be performed prior to dosing. Assessments performed on C2D1 and Day 1 of each subsequent cycle must be performed within 48 hours prior to dosing.
- m. **Coagulation assays:** See Assessments [Section 7.1.3](#) for Laboratory Tests list. No need to repeat on C1D1 if baseline assessment performed within 72 hours prior to that date. Assessments performed on C2D1 and Day 1 of each subsequent cycle should be performed within 48 hours prior to dosing.
- n. **Urinalysis:** Dipstick is acceptable. Microscopic analyses if clinically indicated (eg, only after the second positive dipstick result for heme). If $\geq 2+$ protein on urine dipstick, then collect spot urine sample to calculate UPCR or collect 24hr urine.

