5.4.2. SC Administration (Parts 1 and 2)

Qualified and trained investigator site personnel will administer PF-06801591 at a fixed dose of 300 mg to patients by SC injection to the abdomen. A total volume of 6 mL must be administered subcutaneously for a dose of 300 mg of PF-06801591. Ideally, 3 subcutaneous injections of 2 mL should be administered to the abdomen, although, more injections can be done as needed, in order to have a total volume of 6 mL.

Study drug should be administered to two or more different quadrants of the abdomen (with preference given to the lower quadrants when possible); 1 or 2 injections per quadrant. The maximum number of injections per patient is 8 injections. Refer to [Appendix 9](#) for details on administration of multiple injections to the abdomen. Study staff should refer to the IP Manual for specific instructions on the handling and administration of study drug.

Similar to intravenous dosing, a cycle is defined as the time from Day 1 dose to the next Day 1 dose. Patients will receive a single dose of PF-06801591 on Day 1 of each cycle. If there are no treatment delays, a cycle will be 28 days (+/- 2 days) for SC administration. Each patient may receive PF-06801591 until disease progression, unacceptable toxicity, withdrawal of consent, patient no longer willing to participate in trial, or study termination.

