7.1.3. Laboratory Safety Assessment

Hematology and blood chemistry will be drawn at the time points described in the [Schedule Of Activities](#) and analyzed at local laboratories.

Hepatitis B surface antigen (HBsAg), hepatitis B core antibody (HBcAb), hepatitis C antibody (HCV Ab), and HIV serology testing should be conducted at screening. Other tests may be conducted per standard practice to confirm an active hepatitis or HIV infection.

All laboratory safety assessments conducted on Cycle 1 Day 1 (C1D1) must be completed prior to dosing. If baseline assessments are performed within 72 hours prior to C1D1, there is no need to repeat assessments on C1D1. Assessments performed on Cycle 2 Day 1 (C2D1) and each subsequent cycle should be performed within 48 hours prior to dosing. Investigators may have additional blood tests performed for the purpose of planning treatment administration, dose modification, or following AEs. Day 1 safety laboratory test results need to be reviewed by the investigator prior to dosing at the beginning of each cycle for dosing confirmation and administration rate.

In addition, a serum sample will be collected at pre-dose C1D1. This sample will be utilized as a baseline sample for cytokine measurement should cytokine release syndrome occur. Optional samples for cytokine analysis will be collected throughout the study, as clinically indicated.

Table 4. Laboratory Tests

Hematology	Chemistry	Coagulation	Serology	Immunology	Urinalysis ^a	Pregnancy Test or Postmeno-pausal Status
Hematocrit	ALT	INR/PT	HBsAg, HBcAb ^b	CRP or HsCRP (Part 1 only)	Urine dipstick for urine protein: If positive, collect a spot urine to calculate UPCR or collect 24-hr and microscopic (Reflex Testing).	For female patients of childbearing potential, serum or urine test (sensitivity ≥ 25 mIU/mL); For female postmenopausal patients who have not experienced their menses for at least 12 consecutive months. Serum FSH test at screening only, to confirm post menopause.
Hemoglobin	AST	aPTT or PTT	HCV Ab ^b	TBNK (whole blood, Part 1 only)		
	lactate dehydrogenase (LDH)		HIV serology	Cytokine		
Platelets	Alkaline Phosphatase					
WBC	Sodium					
Absolute Neutrophils	Potassium					
Lymphocytes	Magnesium					
Monocytes	Chloride					
Eosinophils	Total Calcium					
Basophils	Total Bilirubin ^c					
CBC	BUN or Urea				Urine dipstick for urine blood: If positive twice or as clinically indicated perform microscopic analysis (Reflex Testing).	
	Creatinine					

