6.2.2. Safety Endpoints (Part 1 and Part 2)

In safety data tabulations, only data collected during the on-treatment period, defined as on or after the first dose of study treatment, and before the last dose of study treatment + 28 days, or the start of any other anti-cancer therapy, whichever is earlier, will be included. In safety data listings, all collected data will be listed.

Adverse Events

Adverse Events (AEs) will be graded by the investigator according to the CTCAE version 4.03 and coded using the MedDRA.⁴ The focus of AE summaries will be on Treatment Emergent Adverse Events, those with initial onset or increasing in severity after the first dose of study medication. The number and percentage of patients who experienced any AE, serious AE (SAE), treatment related AE, and treatment related SAE will be summarized according to worst toxicity grades. The summaries will present AEs both on the entire study period and by cycle (Cycle 1 and Cycles beyond 1) for overall and each dose. The Safety Analysis Set will be used. Part 1 and Part 2 data will be summarized separately and will also be pooled together for analysis. Pfizer standard on safety data reporting will be followed.

Laboratory Tests Abnormalities

The number and percentage of patients who experienced laboratory test abnormalities will be summarized according to worst toxicity grade observed for each laboratory test for overall and each dose. The analyses will summarize laboratory tests both in the entire study period and by cycle (Cycle 1 and Cycles beyond 1). Shift tables will be provided to examine the distribution of laboratory abnormalities. The Safety Analysis Set will be used.

For laboratory tests without CTC grade definitions, results will be categorized as normal, abnormal high/low or not done.

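### Read literally, the SAP's visit-label rule puts the pre-dose Cycle 2 Day 1 laboratory result in later cycles, so the by-cycle table can understate Cycle 1 laboratory toxicity

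*SAP*

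**What the plan says.** **Assignment rule.** SAP 5.3 categorises all data "based on the scheduled visit at which it was collected", and adds: "These visit designators are predefined values that appear as part of the visit tab in the eCRF". The words about exceptions at the start of that paragraph qualify only the baseline definition, not this rule.

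**The table concerned.** Under SAP 6.2.2, laboratory abnormalities are "summarized according to worst toxicity grade observed for each laboratory test for overall and each dose". They are shown for the entire study period and split into Cycle 1 and cycles beyond 1. The section does not say how a result is allotted to one side of the split.

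**When the sample is drawn.** Protocol 7.1.3 states: "Assessments performed on Cycle 2 Day 1 (C2D1) and each subsequent cycle should be performed within 48 hours prior to dosing". The chemistry footnote in the Schedules of Activities is firmer: "Assessments performed on C2D1 and Day 1 of each subsequent cycle must be performed within 48 hours prior to dosing". Protocol 7.1.3 also has the investigator review Day 1 safety results before dosing.

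**What a cycle is.** In protocol 5.4.2, "a cycle is defined as the time from Day 1 dose to the next Day 1 dose". Section 5.4.1 says the same for IV dosing. SAP 6.1 likewise starts a cycle on the date of its first dose.

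**The concern.** The Cycle 2 Day 1 safety sample is taken after one dose and before the second, so anything it shows arose under Cycle 1 exposure. The dose-to-dose definition places it in Cycle 1, but the visit label places it in Cycle 2. A programmer who follows the only assignment rule the SAP states will tabulate it with the later cycles.

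What is at stake is the timing part of a primary endpoint. SAP 3.1 lists laboratory abnormalities characterised by type, frequency, severity and timing for both parts, and the Cycle 1 versus later split is the only timing display SAP 6.2.2 names for laboratory data. The displacement always runs in the same direction, so a larger sample does not average it out.

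**Working it through.** The plan gives no figure that depends on this rule, so there is nothing to reproduce. The check has three steps.

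**1. Direction.** For one patient and one test, let A be the worst grade among post-dose results carrying a Cycle 1 visit label, g the grade at the pre-dose Cycle 2 Day 1 sample, and B the worst grade among later results.

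| Row | Visit label | Dose-to-dose definition |
|---|---|---|
| Cycle 1 | A | max(A, g) |
| Cycles beyond 1 | max(g, B) | B |
| Entire period | max(A, g, B) | max(A, g, B) |

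Since A ≤ max(A, g), the Cycle 1 entry can only be unchanged or too low. It is too low exactly when g > A. The entry for later cycles can only be unchanged or too high. The entire-period row is the same under both rules. Day 1 samples of Cycle 3 onward stay within the later cycles under either rule, so only one sample per patient matters.

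**2. Share of scheduled draws.** These are the hematology, chemistry and coagulation draws after dose 1 and before dose 2, from the Schedules of Activities.

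| Schedule | Draws | Affected |
|---|---|---|
| Part 2 SC | D8, D15, D22, Cycle 2 Day 1 | 1 of 4 |
| Part 1 SC | D8, D15, D21, Cycle 2 Day 1 | 1 of 4 |

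The Part 1 SC days are read from the column pattern of a table that did not extract cleanly. The Part 1 IV laboratory rows have the same problem, and I rely on no count for IV.

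**3. Share of events (illustration only).** The documents give no laboratory event rates. Assume that first onset is uniform between doses and that each abnormality persists to the next sample. The share first seen at Cycle 2 Day 1 is then

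(day of Cycle 2 Day 1 sample − day of last Cycle 1 draw) / (day of Cycle 2 Day 1 sample − 1).

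- Part 2, nominal days: (29 − 22)/(29 − 1) = 7/28 = 25%.
- Part 1 SC, nominal days: (29 − 21)/28 = 8/28 = 29%.

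The visit windows (±2 days) and a sampling lead of 0 to 48 hours widen these a great deal.

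- Part 2: from (25 − 24)/24 = 4% to (31 − 20)/30 = 37%.
- Part 1 SC: from (25 − 23)/24 = 8% to (31 − 19)/30 = 40%.

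If an abnormality has an assumed true Cycle 1 incidence of 5% to 20%, the nominal Part 2 share moves 100 × 0.05 × 0.25 = 1.25 to 100 × 0.20 × 0.25 = 5 of 100 patients. With the range of shares as well, this becomes 100 × 0.05 × 0.042 = 0.2 to 100 × 0.20 × 0.367 = 7.3. These figures show scale under stated assumptions and do not estimate this trial's data.

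**The case against.** The best reply is that SAP 5.3 is a general labelling sentence, that SAP 6.2.2 never says its split uses the visit label, and that SAP 6.1 and the protocol define cycles by dosing. A sensible programmer might already do the right thing. That is fair as far as it goes, but the dose-based definition in SAP 6.1 sits under treatment administration, while 5.3 covers all data and is the only stated rule for allotting results. The SAP should not leave the choice to the programmer.

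The reply is also right that the effect is modest. Nothing in Part 2 is tested, listings show all collected data, and a patient moves only if the Cycle 2 Day 1 grade exceeds every earlier Cycle 1 grade.

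A reader might infer four stronger things that the documents do not support:

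- **That a quarter of Cycle 1 abnormalities are lost.** One in four is a share of draws. Turning it into a share of events needs the assumptions in step 3.
- **That the table will contradict the DLT review.** DLTs are drug-related AEs, classified after investigator and sponsor review and summarised separately under SAP 6.2.1. The Protocol Summary ends the window at Day 21 (IV) or Day 28 (SC), whereas Cycle 2 Day 1 is nominally Day 22 or 29. A sample drawn on the nominal dosing day is already outside the window, so assigning it to Cycle 1 would not align the two.
- **That an abnormality which ends treatment is counted in a cycle that never began.** Protocol 5.4.5 makes the day of restart Day 1 of the next cycle after a prolonged interruption, and a patient who stops has an end-of-treatment visit. The documents do not establish that such a result carries a Cycle 2 Day 1 label.
- **That ECG and vital signs need the same repair.** SAP 6.2.2 plans by-cycle summaries only for AEs and laboratory tests, and SAP 6.6 summarises ECG changes by visit and time point.

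**Conclusion.** The concern holds for the by-cycle laboratory table. Under the SAP's stated rule, the pre-dose Cycle 2 Day 1 result counts in the later cycles although it follows only the first dose. Cycle 1 laboratory toxicity can be undercounted and cannot be overcounted. It is undercounted for each patient and test whose worst Cycle 1 grade first appears at that sample.

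One of four scheduled draws is affected in Part 2, and one of four in Part 1 SC. The number of patients affected cannot be derived from the documents. The conclusion rests on reading SAP 5.3 as governing the split in 6.2.2 and on sites drawing the sample before dosing as the protocol requires. The entire-period laboratory summary and the DLT and MTD decisions do not change.

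**What to change.** Add to SAP 6.2.2, for by-cycle laboratory summaries only:

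- A result collected before the Day 1 dose of cycle n (n ≥ 2) counts in cycle n−1, judged by date and time. Results before the first dose remain baseline.
- Where no clock time is recorded, scheduled Day 1 safety laboratories are treated as pre-dose, as the protocol requires. Date alone would fail, because a pre-dose sample taken on the dosing day shares the date on which the new cycle starts.
- Unscheduled results, which have no scheduled visit, are assigned by date relative to dosing.

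Keep nominal visits for by-visit displays, and leave the ECG and vital-sign analyses as they are.

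The cost is a short SAP addition and a comparison of sample and dose dates in programming. No new assessments are needed. The documents call for exact collection times for PK samples but do not say so for local safety laboratories. The pre-dose default therefore lets the rule work without asking sites for more data.
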